Extended pre-quit run-in treatment regimen. The standard bupropion regimen involving a one week pre-quit run-in prior to the quit date may be insufficient for maximizing clinical outcomes because: (1) bupropion and its dopaminergic agonist metabolite hydroxybupropion do not reach steady-state concentrations until 5–8 days of treatment;¹⁰⁷ (2) more frequent smoking under bupropion-induced attenuation of nicotine reward may facilitate extinction of smoking behavior and improve bupropion's efficacy;⁷⁰ and (3) bupropion-induced attenuation of anhedonia and some of bupropion's other antidepressant effects often take 3-4 weeks to emerge.⁸¹ The proposed trial will apply a novel 4-week extended pre-quit run-in treatment regimen that may be more sensitive to detecting bupropion's efficacy than the standard 1-week run-in, as evidenced by a prior trial of BUP-300 demonstrating superior quit outcomes with a 4-week (vs. 1-week) pre-quit run-in.⁷⁰

Cessation milestones. PPA amalgamates several distinct milestones of the cessation process that may be underpinned by distinct mechanisms: (1) starting the quit attempt and establishing >24 abstinence vs. avoiding quitting altogether; (2) maintaining continuous abstinence vs. lapsing; and (3) amongst lapsers, recovering abstinence vs. relapse back to regular smoking patterns. In our prior work, BUP-300 improved establishment of abstinence, prevented lapse, but did not shorten time from lapse to relapse among lapsers,¹⁰⁸ and post-quit anhedonia predicted worse outcomes for all three milestones.⁵⁷ Supplemental analyses will test the effect of BUP-450 on milestones to elucidate how this novel treatment exerts its effects in anhedonic smokers (C.7).

Measurement of body fat composition outcomes. For the small subset of cessation trials that do report weight-related outcomes, body weight is the predominant index, which is an unreliable measure of adiposity due to regular fluctuations in water retention and muscle changes that may take place during cessation. In an innovative application of obesity research to smoking, we will use a bioimpedance monitor to accurately index body fat and muscle composition via electrical conductance in a non-invasive 2-min scan. As such, we anticipate greater sensitivity and clinical significance for detect for detecting a pro-metabolic effect of BUP-450.

[figure not shown]
C. APPROACH

C.1 Progress Report for R01-DA26831, Project Period: 8/15/09 – 11/30/13

[figure not shown]

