Recruitment and timeline. We plan 3 months for startup, 9-months for an initial pilot, 31 months for primary trial accrual, 8 further months to complete data collection and follow-ups, and 9 months for analysis and write-up. A pilot study will be done on a subset of participants (randomize N=15 per condition) to refine procedures. The pilot will utilize the same design as the standard trial, with non-essential assessments being abbreviated for logistical purposes. Based on prior work and the efficient phone screening methods,³ we expect 16% to be ineligible at the in-person screening and 13% of consenting subjects to not complete all pre-randomization visits and be replaced. Conservatively estimating 80% eligibility and 85% randomization, 14 second-stage screens per month are needed to obtain the intent-to-treat sample of 300 randomized smokers, which had been obtained our prior 5-year trial³ using the recruitment strategies proposed here. The study will be announced via online, print, and mass media advertisements in the greater Los Angeles metropolitan area. Targeted recruitment will take place through: (1) existing research databases from USC-HEAL and [name] (Co-I; UCLA) Laboratory, which contain contact information for 2000+ daily smokers in the LA metro who wished to be called about future studies; (2) referrals from USC primary care clinics run by [name] (Co-I) and his colleagues; and (3) participants responding to advertisements to other USC-HEAL studies that are eligible for this trial.

Eligibility criteria. Inclusion: (1) Lifetime anhedonia on the PHQ-2; (2) smoking 10+ cig/day for 2+ years; (3) Aged 21-65 (21 is legal age to purchase tobacco in CA); (4) breath carbon monoxide (CO) \geq 10 ppm Exclusion: (a) past year moderate or severe DSM-IV non-tobacco substance use disorder (4+ symptoms); (b) a conservative definition of drug contraindications based on lifetime history of panic, bipolar, psychosis, bulimia nervosa, anorexia nervosa, seizure disorders, suicidal attempt (b) report of past 90-day suicidal ideation and alco-

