Week = from quit day (0). Ax = Assessment. F/U = follow-up. R = Randomization. Tx = *Visit by can be by phone. **Additional baseline measures (see C.6). ***Body adiposity scan

Medication. Formulation. Bupropion XL 150mg, and placebo tablets matching in appearance (Rejuvination Labs, San Diego, CA) will be used. **Regimen.** The selected regimen was based on medication guidelines¹⁸¹ and evidence that a 4-week extended run-in prior to quit day produces superior outcomes relative to the standard 1-week run-in,⁷⁰ All dosing is once per day per XL formulation guidelines.¹⁸² BUP-450 involves a 17-day up-titration (1 x 150 mg tablet for 3 days followed by 2 x 150 mg tablet for 14 days), 10-day pre-quit run-in (3 x 150 mg tablets), 8-week post-quit treatment period (3 x 150 mg tablets), and 1-week down-titration (2 x 150 mg tablet). The BUP-300 regimen is identical except that pre-quit run-in and 8-week post-quit treatment period involves 1 x placebo + 2 x 150mg to match number of tables taken across conditions and differentiate dose. **Clinical monitoring/safety:** In addition to eligibility screen, participants will meet with the physician at: (a) treatment outset to review the medication, managing and/or reporting side effects, pregnancy contraindications, and rationale for taking the medication for ≥ 4

weeks prior to quitting; and (b) end of treatment to review treatment, collect labs, and discuss down-titration. All participants will be given a 24-hour phone number and physician office hours will be available as needed. Vital signs, weight, and side effects, including suicidal ideation, will be monitored at each study visit. In the event that significant medical problems are encountered, the blind will be broken and appropriate medical treatment will be provided.

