Cessation counseling. All participants will be offered bibliotherapy (NCI- Clearing the Air)¹⁸³ and receive seven 10-20 min sessions based on the USDHHS clinical practice guidelines. Trained counselors (blind to treatment), supervised by [name], a licensed clinical psychologist, will provide the counseling, which focuses on enhancing social support, problem solving, coping skills, and check-ins on medication adherence. Three pre-quit visits focus on establishing the quit-date and preparation. Four post-quits focus on reinforcing abstinence (or encouraging the resumption of cessation) and continued support. There is a final check-in at the end of the medication treatment period. Some visits will be offered via phone (Table).

C.6 Measures (see Table for the assessment schedule).

Screening and baseline measures. (1) Medical history interview for bupropion contraindications; (2) Physical exam; (3) Blood and urine for liver/kidney function, drug screen, and pregnancy; (4) EKG to rule out unstable cardiovascular disease; (5) Clinical Institute Withdrawal Assessment for Alcohol¹⁸⁴ to rule out alcohol-related seizure risk (score ≥ 10); (6) Structured Clinical Interview for DSM-5 (SCID) modules for diagnostic rule outs and other Axis-I disorders for descriptive purposes (PTSD, MDD, Dysthymia, Social Anxiety, ADHD)¹⁸⁵; (7) Tobacco Product Use History Questionnaire (e.g., age of onset, cig/day, use of other tobacco products, etc.); (8) FTND;¹⁷⁹ (8) Ten-Item Drug Abuse Screening Test (DAST-10)²⁰³, with no record made regarding specific names of drugs used, and (9) Premenstrual Symptoms Impact Survey¹⁸⁶ and date of last menstruation, given evidence that these factors influence quit outcomes¹⁸⁷ will be used in supplemental sex-specific analyses (C.7).

Core assessments (all in-treatment visits). To aid counselors' intervention, collect cessation milestone outcomes (C.7), and to monitor safety, we will administer: (a) smoking timeline follow-back to track smoking,¹⁸⁸ (b) 8-item Minnesota Nicotine Withdrawal Scale,¹⁸⁹ (c) Systematic Assessment for Treatment Emergent Events¹⁹⁰ and open ended reports coded by Medical Dictionary for Regulatory Activities Version 14.0.

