Primary Aim 2: Mediation. Aim 2 will examine slopes from individual piece-wise LGCMs (or raw difference scores when only 2 timepoints available) to model changes in reward processing (see C.6) prior to quit day, the jump from pre to 1-week post-quit, and post-quit changes. A latent variable framework using Mplus 7.4 will allow estimates of treatments on individual growth in mediators (path 'a') to be modeled jointly with effects of growth in likelihood of abstinence (path 'b') using models that limit bias in estimates and provide accurate evaluation of mediation using bias corrected effect estimation and product of coefficients procedures. We will attempt to create a composite that amalgamates all reward processing mediators using principal component analysis (PCA), or if a strong component is not detected, test each raw variable individually. We will model time to lapse first and other smoking outcomes secondarily with and without smoking as a time-vary covariate. Additional multiple mediator models adding all 3 growth pieces simultaneously and including the discriminant constructs (negative affect, urge to smoke to alleviate negative affect) will be test the specificity of effects.

Secondary Aims: Aim 3 will examine medication effects on anhedonia (SHAPS) and related psychopathology (i.e., depressive, social anxiety, ADHD, PTSD symptoms) and body weight and body fat percentage trajectories using individual growth models (intercept and slope) of assessments at visits during treatment. Moderation of the differential effect of treatment (Aim 4) will be assessed with interaction terms of treatment condition and corresponding moderators (SHAPS, depressive, social anxiety, ADHD, PTSD symptoms) in successive models as described above in LGCM.

Supplemental analyses of the biological variable of sex and other characteristics (age, ethnicity/race). Using the strategies above, we will examine if sex, ethnicity/race, and FTND moderate treatment effects on primary and secondary outcomes. We will report sex-stratified analyses and test, amongst women, whether days since menstruation at the onset of treatment and quit day moderates outcome using several classification methods (follicular vs. luteal; early follicular vs. late follicular vs. mid luteal vs. other).

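### Cycle day on quit day is a planned moderator, but the date of last menstruation is listed only at screening/baseline, at least about four weeks earlier (minor; supplemental analysis)

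*Combined protocol and SAP*

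**What the plan says.** The supplemental sex analyses in C.7 (Analytic Plan) will test "whether days since menstruation at the onset of treatment and quit day moderates outcome using several classification methods". Two classifications are named: "follicular vs. luteal; early follicular vs. late follicular vs. mid luteal vs. other". No day limits are given for any phase.

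The data source is item (9) of the screening and baseline measures in C.6, a premenstrual symptom survey "and date of last menstruation, given evidence that these factors influence quit outcomes". That item is earmarked for the sex-specific analyses in C.7. The date does not reappear in the lists of core, supplemental or outcome assessments. The list headed "Core assessments (all in-treatment visits" contains a smoking timeline, a withdrawal scale and adverse-event reporting.

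In the C.5 schedule, "Additional baseline measures (see C.6" is the footnote to the pre-randomization column. The time axis is "Week = from quit day (0", and the first treatment visit is week -4. Section B says: "The proposed trial will apply a novel 4-week extended pre-quit run-in treatment regimen".

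The C.4 age criterion is "Aged 21-65 (21 is legal age to purchase tobacco in CA". The only reproductive exclusions are current or planned pregnancy and breastfeeding. C.7 has no rule for postmenopausal women, hormonal contraceptive users or irregular cycles, and no method for carrying a cycle date forward.

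**The concern.** The moderator is dated at two points, and one of them is quit day. The only listed menstruation date is about one full cycle old, or older, by then. Counting days from it does not give days since the latest menses, because another has usually begun. The analyst would have to project with an assumed cycle length, which brings error into the phase label. The correct date cannot be recovered reliably after the trial.

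Separately, some women aged up to 65 will have no natural cycle. Without a stated subset, the analyst has to decide after the data are in whom to classify.

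At stake is the interpretability of one supplemental moderator test, chiefly its quit-day half.

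**Working it through.** The plan gives no sample size, power or error rate for this analysis, so there is no figure of its own to reproduce.

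**Timing (from the documents).** The C.5 titration and run-in take 17 + 10 = 27 days, in line with the 4-week (28-day) run-in. Baseline comes before week -4 by an unstated interval. The lag from the recorded date's visit to quit day is therefore at least about 28 days. I take 28-42 days, which assumes 0-14 days from baseline to treatment start.

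**Is a new menses likely before quit day?** A woman on day *d* of a cycle of *c* days has a new menses within 28 days if *d* + 28 ≥ *c*. With *c* ≤ 28 this is certain. With *c* > 28 and *d* uniform, the share without one is (*c* - 28)/*c*, for example (32 - 28)/32 = 12.5% at a 32-day cycle.

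**Size of the error.** Simulation of 400,000 women per setting. Assumptions, none of them in the documents: independent cycle lengths with mean 28 days and the SD shown, baseline at a uniformly random cycle day, and true luteal phase equal to the last 14 days of the cycle. The projected label is luteal if (days since the recorded menses mod 28) ≥ 14. The comparison label uses the actual days since menses on quit day, with the same cut at 14. Ranges cover lags of 28-42 days.

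| Within-woman SD (days) | New menses before quit day | Projected phase wrong | Wrong with a quit-day date |
|---|---|---|---|
| 1 | 99-100% | 7-8% | 3% |
| 2 | 97-100% | 15-17% | 6% |
| 3 | 96-100% | 22-25% | 8-9% |
| 4 | 95-100% | 29-33% | 11-12% |

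A mean of 29 days with SD 4 and a 42-day lag gives 35%, so I summarise the projected error as roughly 7-36%. Adding between-woman variation of SD 3 at a mean of 29 raises the upper end to 42%.

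Phase at treatment onset, projected from the same baseline date, is wrong in 4-28% over the range that ends at 42% for quit day. The four-class scheme does worse, but its error depends on cut-points that the plan does not give. One assumed set gave 18-67% on quit day.

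**Women without a cycle.** If ages were uniform over 21-65 (assumed), the share above a cut-off age *a* is (65 - *a*)/44:
- *a* = 55: 10/44 = 23%
- *a* = 50: 15/44 = 34%
- *a* = 45: 20/44 = 45%

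C.4 expects balance on sex, so about 150 of the 300 randomized would be women. That leaves about 116, 99 or 82 women to classify, before hormonal contraceptive users are removed.

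**The case against.** The strongest defence is that this is one clause of a supplemental analysis, with no stated hypothesis or power, outside Aims 1-4. That stands and sets the severity. It is also fair that the single collection point is inferred from the measure lists. The documents do not say the date will not be asked again. But C.6 names the baseline item as the input to C.7 and lists no other, so following the plan as written gives only the one date.

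Several stronger readings are tempting but not supported:

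- *Quit-day phase is largely misclassified or undefined.* Combining the age shares with the two-class error gives 0.23 + 0.77 × 0.07 = 0.28 to 0.45 + 0.55 × 0.36 = 0.65. Whether that is most women depends wholly on assumptions outside the documents. With regular cycles, projection is right in about 93% of cycling women.
- *Non-cycling women will be counted as luteal or other, confounding phase with age.* The text does not say so. They might equally be left unclassified. What can be said is that no rule is stated.
- *Nothing in C.6 captures menopause or contraception.* The medical history interview and physical exam are not itemised and might. Neither is listed as an item for this analysis.
- *The error pulls any phase-by-dose interaction towards zero, so the sex analyses can support no conclusion.* Attenuation is the usual expectation for two classes, but individual contrasts among four classes can be biased either way. Where attenuation is the only bias, a detected interaction is still informative. Sex as a moderator and the sex-stratified results use no menstrual data.

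**Conclusion.** The mismatch between C.6 and C.7 is real. Under the listed schedule, cycle day on quit day is not observed for nearly all cycling women. About 95-100% have a new menses first under a 28-day mean cycle with SD 1-4 days. If phase is projected, the two-class label is wrong in roughly 7-36%, against about 3-12% with a date taken on quit day. These percentages rest on assumed cycle lengths, an assumed baseline-to-quit lag of 28-42 days and a fixed 14-day luteal phase. That the date is at least about four weeks old rests on the documents alone. The missing rule for women without a natural cycle is a second, smaller gap. Phase at treatment onset is less affected. The primary abstinence analysis, its sample size and the remaining sex analyses are untouched. Severity is minor.

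**What to change.** In C.6 and the C.5 schedule, ask the date of last menstruation again at the week -4 and week 0 visits. Both already carry core assessments, and neither is marked as a phone visit. Record menopausal status and current hormonal contraceptive use as baseline items.

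In C.7, add that the phase analysis is limited to naturally cycling women and uses the date collected nearest each time point. Days since menstruation is then observed at both points and no projection is needed.

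The cost is one question repeated at two existing visits, two baseline items and one sentence in C.7. The downside is a smaller analysed group: about 82-116 of 150 women (41-58 per arm) under the uniform-age assumption, and fewer once hormonal contraceptive users are removed. The analysis should be reported as exploratory at that size.

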Bupropion is an anti-depressant that increases striatal dopamine transmission,¹⁰ improves reward processing¹⁰ and is widely available at a modest cost.¹¹ The standard 300 mg/day dose of bupropion has demonstrated clear efficacy for smoking cessation in various populations.^{12,13} Outside of the smoking literature, high dose bupropion (400-450 mg/day) exhibits superior efficacy relative to the 300 mg/day dose for treating psychiatric disorders,^{14,15} reducing weight and body fat,¹⁶ and alleviating anhedonia,¹⁴ without meaningfully increasing side effects.¹⁷ Thus, high dose bupropion may be particularly effective at promoting smoking cessation in anhedonic smokers, improving anhedonia-related mental health, and preventing post-quit weight gain. To the best of our knowledge, 300 mg/day is the highest bupropion dose tested for smoking cessation in any population to date.

In this continuation proposal, we translate work in the prior period on mechanisms underlying relapse in anhedonic smokers to the development of a novel, disseminable, and putatively effective treatment for this high risk population. We propose a clinical trial in which anhedonic smokers are provided standard cessation counseling and randomized to either: the standard 300 mg/day dose of bupropion (BUP-300; N=150) or a high 450 mg/day dose (BUP-450; N=150). In addition to treatment effects on 7-day point prevalence smoking abstinence (PPA) outcomes, we will: i) examine if improvement in reward processing is a mechanism of action for BUP-450's efficacy with innovative laboratory-based computer task and subjective indices of reward processing, ii) assess moderators of treatment efficacy, iii) investigate treatment effects on secondary mental health and body weight and adiposity outcomes; and iv) utilize the extended release (XL) formulation that requires dosing only once per day, which has yet to be tested for cessation and may increase adherence.

Primary Aims

- 1. To test the efficacy of high dose bupropion for smoking cessation in anhedonic smokers.** Hyp 1. PPA rates across the 6-month post-quit follow-up period will be higher in BUP-450 vs. BUP-300.

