- 2. To test whether treatment-related enhancement of reward processing is a mechanism of action of high dose bupropion.** Hyp 2. The effects of BUP-450 vs. BUP-300 cessation outcomes will be mediated by reward processing, such that dose will predict greater improvements in reward processing, which will in turn be associated with greater odds of abstinence.

Secondary Aims

- 3. To test the effects of high dose bupropion on secondary outcomes of:** (a) anhedonia and related psychopathology (i.e., depressive, social anxiety, ADHD, PTSD symptoms), and (b) change in body weight and percent body fat composition.
- 4. To examine if baseline anhedonia level and related psychopathology (depressive, social anxiety, ADHD, PTSD symptoms) moderate the efficacy of high dose bupropion on cessation outcome.**

If successful, this research may identify a novel, highly-disseminable, cost-effective, and efficacious cessation treatment for an at-risk population, with wide-spanning implications toward offsetting three of the nation's top causes of morbidity and mortality—smoking, mental illness, and health problems due to excessive weight.

A. SIGNIFICANCE

A.1 Importance of Increasing Cessation Treatment Outcomes for Smokers Psychiatric Symptoms

While the overall population-level rate of smoking has significantly declined in recent years, smoking among those with psychiatric symptoms and conditions has remained stable,¹⁸ with SWPS accounting for a mounting proportion of the U.S. tobacco-related disease burden each year.¹ A key source of the tobacco-related health disparities facing SWPS is their disproportionately low quit rates.¹ Hence, improving smoking cessation among SPWS is vital for reducing tobacco-related disparities and counteracting the public health burden of smoking.

A.2 Current Status of Cessation Treatment Development Research for SWPS

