relapse curves in anhedonic smokers, BUP-450 vs. BUP-300 vs. PLA effects on weight loss and mental health.^{22,97,162} We generated 1,000 multivariate normal random samples of correlated binary outcomes using covariance estimates from prior trial data (range 0.55-0.25)³ and analyzed the datasets using LGCM focusing on the proportion of significant ($p < 0.05$) values for each pair-wise contrast (Aim 1). The percentage of datasets with significant effects for each hypothesis (i.e., $>80\%$ of $ps < .05$) provided a simulation-based estimate of power. Using this technique, we found that enrolling a sample size of 375 (BUP-450: $N < 150$, BUP-300 $N < 150$) conservatively would have power >0.83 to detect main effects when testing our primary hypothesis, allowing for 20% attrition among those enrolled. Parallel simulations were conducted using LGCM to assess power for growth trajectories in continuously scaled mediators assuming an effect of treatment dose response on reward processing ($ds > 0.3$), and reward processing on outcome ($ds > 0.17$) based on the prior literature.^{131,140,201,202} We also found support for power >0.81 with average effects of 0.31 ($sd = 0.11$) with $N = 375$. Additional simulations for secondary mental health and body/weight adiposity outcomes based effects in prior literature ($ds > 0.3$)^{22,97,162} yielded adequate power ($> .80$). Missing individuals will be presumed to have continued smoking. All analyses will use an intent-to-treat approach.

REFERENCES

4. [name] AM, Zvolensky MJ. Anxiety, depression, and cigarette smoking: A transdiagnostic vulnerability framework to understanding emotion-smoking comorbidity. *Psychological bulletin*. 2015;141(1):176.
5. Gorwood P. Neurobiological mechanisms of anhedonia. *Dialogues Clin Neurosci*. 2008;10(3):291-299.

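### The Aim 2 power above 0.81 is stated for N=375 and an unnamed parameter; at the planned 300, power for the indirect effect is about 0.62 to 0.70, or 0.2 to 0.3 on another reading of 0.17

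*Combined protocol and SAP*

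**What the plan says.** Primary Aim 2 (Specific Aims) is a mediation hypothesis: "The effects of BUP-450 vs. BUP-300 cessation outcomes will be mediated by reward processing". Dose must improve reward processing (path a), and that improvement must in turn relate to abstinence (path b).

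C.8 gives the Aim 2 simulation two inputs, "assuming an effect of treatment dose response on reward processing ($ds > 0.3$), and reward processing on outcome ($ds > 0.17", and reports one result: "We also found support for power >0.81 with average effects of 0.31" (sd 0.11), at N=375. It describes the exercise as power for the mediators' growth trajectories. It does not say whether the tested parameter was path a, path b or their product.

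C.7 (Primary Aim 2) plans to test mediation by bias-corrected estimation with the product of coefficients, in a piecewise latent growth curve model (LGCM) that takes time to lapse as the leading outcome.

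On sample size, the Specific Aims randomize to "bupropion (BUP-300; N=150) or a high 450 mg/day dose (BUP-450; N=150" per arm, and C.4 also gives an intent-to-treat sample of 300. C.8 allows for 20% attrition, and 300/0.8 = 375, yet it shows 375 beside arms of fewer than 150 each.

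**The concern.** A single power figure stands behind a hypothesis that needs two effects together. It is quoted at a sample size 75 above the number to be randomized, and the effect printed next to it is far larger than the product of the two assumed effects.

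The stake is how a null result would be read. With stated power above 0.81, a non-significant indirect effect invites the conclusion that reward processing is not how the higher dose works. If the real power is 0.62 to 0.70, a true mediated effect of the assumed size is missed 30% to 38% of the time, against the 19% or less that the plan implies. On the less favourable reading of 0.17, it is missed 70% of the time or more.

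**Working it through.** **Inputs.** From C.8: path a, d = 0.30 (0.31 as the printed average); path b, 0.17; N = 375; attrition 20%. From the Specific Aims and C.4: 300 randomized, 150 per arm. Assumed: two-sided alpha of 0.05 (C.8 gives 0.05 for Aim 1 and no sidedness for Aim 2), one mediator, a continuous outcome, and the assumed effects taken at their stated lower bounds.

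**Step 1: reproduce the plan's figure at N=375.**
- Path a, two-sample t-test with noncentrality d x sqrt(N)/2: 0.30 x sqrt(375)/2 = 2.90, power 0.83; with d = 0.31, 0.85.
- The printed effect and sd, read as estimate and standard error: 0.31/0.11 = 2.82, and Phi(2.82 - 1.96) = 0.80.
- Product a x b by bias-corrected bootstrap, 0.17 as a standardized coefficient (10,000 simulated datasets, 1,000 resamples each): 0.82 with a = 0.30, 0.83 with a = 0.31.

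So the power figure alone fits either path a or a bias-corrected test of the product.

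**Step 2: compare the printed effect and sd.** Simulating a = 0.30 and b = 0.17 at N=375:

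| Parameter | Mean | SD | Mean/SD |
|---|---|---|---|
| Path a | 0.30 | 0.10 | 2.92 |
| Path b | 0.17 | 0.05 | 3.30 |
| Product a x b | 0.05 | 0.02 | 2.15 |
| C.8 as printed | 0.31 | 0.11 | 2.82 |

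Only path a matches in both size and ratio.

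**Step 3: power at the planned N, 0.17 as a standardized coefficient.** Path b power is Phi(0.17 x sqrt(N) - 1.96). At N=300: 0.17 x sqrt(300) = 2.94, power 0.84. Joint significance is the product of the two path powers: 0.738 x 0.838 = 0.62 (0.738 is the normal approximation for path a; the t-test gives 0.736).

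| Test (a = 0.30) | N=375 | N=300 | N=240 |
|---|---|---|---|
| Path a alone | 0.83 | 0.74 | 0.64 |
| Path b alone | 0.91 | 0.84 | 0.75 |
| Indirect, Sobel | 0.59 | 0.50 | not run |
| Indirect, percentile bootstrap | 0.74 | 0.59 | 0.44 |
| Indirect, joint significance | 0.75 | 0.62 | 0.48 |
| Indirect, bias-corrected bootstrap | 0.82 | 0.70 | 0.56 |

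With d = 0.31, path a alone at N=300 is 0.76. N=240 is 300 x 0.8, which applies if the attrition falls on the 300.

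**Step 4: 0.17 as Cohen's d.** C.8 labels it that way. The equivalent correlation is 0.17/sqrt(0.17^2 + 4) = 0.085. Path b power by Fisher's z is then 0.37 at N=375 and 0.31 at N=300. For the indirect effect, joint significance gives 0.31 and 0.23, and the bias-corrected bootstrap 0.40 and 0.30.

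**Step 5: error rate of the bias-corrected test.** With one path set to zero at N=375, it rejected about 7% of the time against a nominal 5%. Part of its advantage in Step 3 comes from this.

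**The case against.** The strongest reply is that C.8 may already be right at its own sample size. C.7 points to a bias-corrected test of the product, and that test gives about 0.80 to 0.82 at N=375 with the plan's inputs. This stands. A reader might infer that the figure above 0.81 can only be path a, or that no test of the indirect effect reaches 0.81 even at 375. The documents do not support either inference: C.8 lists both assumed effects before giving its result, does not name the parameter, and does not define the 0.11 as a standard error. Step 2 makes path a the better-supported reading, not an established one.

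The plan also gives its effects as lower bounds, so larger true effects would raise power. A one-sided test of path a would give about 0.83 at N=300, but C.8 does not call the test one-sided, and path a alone is not Hypothesis 2.

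The N=240 column is a worst case. Because 375 = 300/0.8, C.8 may already have spent its attrition allowance in reaching 375, and the missing-data plan uses all available observations and multiple imputation. That reading does not rescue the figure: if 300 were the number analysed, path a alone gives 0.74 to 0.76 two-sided.

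Finally, all these values come from a simpler model than the planned LGCM with time to lapse, so no single number should be imposed on the sponsor. That also stands, and it is why a range and a re-run are requested.

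**Conclusion.** The concern holds as a mismatch in sample size combined with an unnamed parameter and an undefined scale. It does not show that the simulation was miscalculated at 375. At the 300 to be randomized, every two-sided test tried falls short of 0.81: about 0.74 to 0.76 for path a alone; about 0.62 (joint significance) to 0.70 (bias-corrected) for the indirect effect if 0.17 is a standardized coefficient, with Sobel and percentile limits lower still; and about 0.2 to 0.3 if 0.17 is Cohen's d. If 20% of the 300 were lost without recovery, the standardized-coefficient figures would be about 0.48 to 0.56.

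These values rest on two-sided alpha of 0.05, one mediator, a continuous outcome and effects at the plan's lower bounds. The shortfall at 300 does not depend on which parameter was powered; its size depends mainly on the scale of 0.17, which only the sponsor can supply.

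**What to change.** In C.8:
- Replace the Aim 2 figure with the power of the indirect effect at 150 per arm, from a re-run of the existing simulation using the test that C.7 names.
- State the scale on which 0.17 is measured.
- State whether the 20% attrition is taken from the 300 randomized or was already used in reaching 375.
- If the figure above 0.81 was for path a only, say so.

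In the reporting of Aim 2, give the indirect effect with its interval, and do not treat a non-significant result as absence of mediation on the strength of the figure now stated. Aim 2 can remain a primary, hypothesis-testing aim; recasting it as estimation would be a matter of preference.

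The cost is one re-run, a few sentences in C.8 and a less favourable stated power. No extra patients are needed.
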